16.3 New York Heart Association (NYHA) classification

Table 16–3: New York Heart Association (NYHA) categories

Class	Patients have cardiac disease but without the resulting limitations of physical activity. Ordinary physical activity does not cause undue fatigue, palpitation, dyspnea, or anginal pain.		
I			
II	Patients have cardiac disease resulting in slight limitation of physical activity. They are comfortable at rest. Ordinary physical activity results in fatigue, palpitation, dyspnea, or anginal pain.		
III	Patients have cardiac disease resulting in marked limitation of physical activity. They are comfortable at rest. Less than ordinary physical activity causes fatigue, palpitation, dyspnea, or anginal pain.		
IV	Patients have cardiac disease resulting in inability to carry on any physical activity without discomfort. Symptoms of cardiac insufficiency or of the anginal syndrome may be present even at rest. If any physical activity is undertaken, discomfort is increased.		

23 MAY 2023 Version 6.0 Page: 181 of 181

16.4 Estimated glomerular filtration rate (eGFR) calculation

In accordance with established nephrology practice and guidelines, renal function at baseline and throughout the study will be assessed by means of the estimated Glomerular filtration rate (GFR), calculated using the Modification of Diet in Renal Disease (MDRD) study abbreviated formula.

This equation of 4 variables (serum creatinine level [SCR], age, sex, and race) is recommended by the National Kidney Foundation for use in individuals 18 years or older.

The GFR calculator can be found at the following website (43): http://www.kidney.org/professionals/kdoqi/gfr calculator.

Note: This equation should be used only with those creatinine methods that have not been recalibrated to be traceable to isotope dilution mass spectroscopy (IDMS).

The above result should be multiplied by 1.212 for African-Americans, and by 1.227 for Chinese (mainland China, Taiwan and Hong Kong). Due to the lack of confirmed information on Korean patients the results for these patients will not be multiplied by any factor (44).

SD	Stable disease
TA	Tumor assessment
TCGA	The Cancer Genome Atlas
TEAE	Treatment-emergent adverse event
TEADR	Treatment-emergent drug-related adverse events
TNM	Classification of Malignant Tumors (T = tumor, N = lymph node, M = metastasis)
t_{last}	Time of last plasma concentration above LLOQ
t_{max}	Time to reach C_{max} (in case of two identical C_{max} values, the first t_{max} will be used)
UPM	Unit probability mass
W	White
WHO-DD	World Health Organization – Drug Dictionary

1. Introduction

This Statistical Analysis Plan (SAP) is based on the Clinical Study Protocol No. BAY 1163877 / 19131, Version 4.0, dated 04 OCT 2021 [1].

The study 19131 is planned to evaluate the safety, tolerability, pharmacokinetics (PK) and efficacy of oral twice daily rogaratinib in combination with atezolizumab in subjects with fibroblast growth factor receptor (FGFR)-positive locally advanced or metastatic urothelial carcinoma who are cisplatin-ineligible and have had no prior systemic treatment for locally advanced or metastatic disease.

Urothelial cancer is a highly immunogenic tumor, in large part as a result of the relatively high level of mutations, which represents at least one of the mechanisms for the generation of tumor neo-antigens for the host immune system to recognize. Programmed death-ligand 1 (PD-L1) overexpression in the tumor microenvironment and its binding to programmed death protein 1 (PD-1) on tumor antigen-specific T cells is a mechanism for immune escape in urothelial cancer.

Dysregulation of FGFRs has been identified in bladder cancer as compared with normal bladder. Increased expression was associated with mutation, 85% of mutant tumors showed high level expression, overall 42% of tumors with no detectable mutation showed over-expression including many muscle invasive. This may represent a non-mutant subset of tumors in which FGFR3 signaling contributes to the transformed phenotype and which may benefit from FGFR-targeted therapy.

It was shown that FGFR3 expression is associated with a non-T-cell-inflamed phenotype in tumor tissue of subjects with urothelial bladder cancer. Expression analysis of PD-L1 in archival biopsy samples collected in study 16443, showed that PD-L1 level is lower in subjects with FGFR mRNA overexpression. A similar correlation was detected in subjects with non-small-cell lung carcinoma using publically available TCGA data sets. It is assumed that a causal relationship between FGFR expression and T-cell exclusion leads to the observed findings and to a poorer response to inhibition of the PD-L1 axis by recently approved checkpoint inhibitors. Potentially, inhibition of FGFR can overcome this interaction and render tumors targetable by the immune system.

Atezolizumab is a PD-L1 antibody that demonstrated durable responses in urothelial bladder cancer as first-line and second-line treatment for subjects with locally advanced or metastatic urothelial carcinoma. It is assumed that subjects with FGFR overexpression exhibit a poorer response to atezolizumab treatment based on the non-T-cell-inflamed phenotype. Therefore it is suggested, that a combination of rogaratinib and atezolizumab can overcome this immune evasion improving immune-checkpoint inhibitor efficacy and disease response.

2. Study Objectives

Study 19131 originally comprised two separate parts: Phase 1b (Part A) and Phase 2 (Part B). The study parts differ in design, objectives, and treatment. Part B of the study will no longer be conducted.

The primary objectives of this Part A of the study are:

- To determine the safety and tolerability of rogaratinib in combination with atezolizumab in subjects with FGFR-positive locally advanced or metastatic urothelial carcinoma.
- To determine the recommended Phase 2 dose (RP2D) of rogaratinib in combination with atezolizumab in this subject population.

The secondary objectives of this Part A of the study are:

- To assess the efficacy of the combination of rogaratinib and atezolizumab in this subject population.
- To characterize the PK of rogaratinib in combination with atezolizumab in this subject population.

The exploratory objectives of this Part A of the study are:

- To assess new potential predictive or prognostic biomarkers and their association with tumor-related biomarkers, disease response, drug-resistance and subject outcome.
- To evaluate further biomarkers to investigate the drug (i.e. mode-of-action-related effect and / or safety) and / or the pathomechanism of the disease.
- To evaluate the combination of rogaratinib and atezolizumab with regard to subject-reported outcomes (PRO).

3. Study Design

This study 19131 Part A is an open-label, single-arm, international, multicenter, Phase 1b study of rogaratinib in combination with atezolizumab in subjects with FGFR-positive locally advanced or metastatic urothelial carcinoma.

The primary objectives of this Phase 1b study (Part A) are to determine the safety, tolerability, RP2D and PK of rogaratinib in combination with atezolizumab in these subjects. For all study objectives, see Section 2.

Before entering the screening, subjects are to be tested for FGFR1 and 3 mRNA expression levels. Only subjects with FGFR-positive tumors (RNA scope score of +3 or +4) can enter the study.

The study will comprise the following periods:

- Pre-treatment period, including FGFR testing and screening,

Statistical Analysis Plan Supplement

BAY 1163877/19131 Part A

Page: 6 of 18

- Treatment period, and
- Follow-up period, including active follow-up and long-term follow-up.

[figure not shown]
An overview of the study design is presented in [Figure 3-1](#).

The study is conducted in subjects who are cisplatin-ineligible and have had no prior systemic treatment for locally advanced or metastatic disease.

Treatment is divided into cycles. A cycle consists of 21 days of BAY 1163877 twice daily.

Subjects will receive rogaratinib plus atezolizumab combination treatment.

Figure 3-1: Study 19131 Part A – Design overview

FGFR = Fibroblast growth factor receptor

a: Only FGFR positive subjects can enter screening.

b: Safety information is collected for all discontinued subjects for at least 30 (up to +7) days after the last administration of study treatment, and both safety and efficacy information is collected for subjects who discontinue study treatment without radiological disease progression.

Dose selection

The dose selection part of the study 19131 will assess the safety and tolerability of the combination. The maximum tolerated dose (MTD) will be determined by using stepwise dose selection design based on a modified toxicity probability interval (mTPI) method. Dose selection will stop after 20 valid subjects are available, and are evaluable for the MTD assessment. At the end of the DLT observation period of 20 subjects, the recommendations from the mTPI method will be regarded as guidance and will be integrated with the clinical assessments of the available PK and safety data to determine the MTD. A total of approximately 26-30 evaluable subjects will be enrolled to obtain additional safety data for confirming the MTD and to determine the RP2D that will be used in the Part B of the study.

The mTPI provides a practical dose-finding scheme guided by the posterior inference for a simple Bayesian model. The MTD is defined as the highest dose level that could be given so that the toxicity probability is closest to 30%. The starting dose of rogaratinib will be 800 mg b.i.d. Initially, at least 4 (4-6) subjects will be enrolled. The next group of subjects will be enrolled once the decision regarding the next dose level is made based on all available PK and safety data and the occurrence of DLTs. The decision about time of enrollment and the number of subjects evaluable for DLTs on a dose level will be made by the sponsor in consultation with investigators during regularly held safety calls. For details on what constitute DLTs, please refer to Section 7.4.3.1 of the protocol.

Safety will be regularly assessed during each cycle for potential adverse events, DLTs and disease-related signs and symptoms. Rogaratinib dosing will be interrupted/delayed or reduced in case of clinically significant toxicities. Atezolizumab dosing will not be adjusted,

however dosing will be interrupted or delayed in case of clinically significant toxicities. For more detailed information on dose modifications see Section 7.4.3 of the protocol.

The mTPI method will recommend de-escalation, re-escalation or expansion of the current dose level on basis of the observed DLTs. The first dose finding action on a dose level will be performed after at least 4 subjects are available on that dose level and are evaluable for DLTs. The possible dose finding actions are ‘E’=escalate to next higher dose level (800 mg b.i.d. being the highest possible dose), ‘S’=stay at the current dose level, ‘D’=de-escalate to next lower dose level and ‘DU’= de-escalate to next lower dose level and exclude the current and higher dose levels from the further dose escalation due to unacceptably high toxicity. If the probability that a dose is above the MTD is greater than 95%, the dose will be declared as toxic and only lower doses will be given in subsequent cohorts. If the highest dose is reached, escalation (‘E’) leads to staying at that dose. At the lowest dose level de-escalation (‘D’) or de-escalation with unacceptable high toxicity (‘DU’) lead to stop of the study. Details are provided in Section 6.4.1.

Intra-subject dose escalation is not permitted. Part B will start once safety and efficacy data are found to support study continuation.

4. General Statistical Considerations

4.1 General Principles

The statistical evaluation will be performed by using the software package SAS release 9.2 or higher (SAS Institute Inc., Cary, NC, USA).

All variables will be analyzed by descriptive statistical methods. The number of data available and mean, standard deviation, minimum, median, and maximum will be calculated for metric data. Frequency tables will be generated for categorical data.

Due to the exploratory character of this Part A of the study, no confirmatory analysis will be performed. All calculated p-values and confidence intervals are to be interpreted in the exploratory sense.

Data displays will follow the standard table catalogs for oncology standards, global standards, and clinical pharmacology standards, respectively.

All summaries will be performed by dose group. The dose groups “Rogaratinib XX mg BID+ Atezolizumab” will be analyzed, in which “XXmg” stands for the assigned dose. Pooled summary statistics (or frequency counts) will be provided where appropriate. Listings will also be provided by dose group.

4.2 Handling of Dropouts

Pre-screening failure = Subject signed ICF for FGFR testing but, for any reason, did not sign the ICF for study treatment eligibility.

Screening failure = Subject signed ICF for study treatment eligibility but, for any reason (e.g. failure to satisfy the selection criteria), terminated the study before start of study treatment.

Dropout = Subject discontinued study participation prematurely for any reason after start of study treatment. The start of the treatment period is defined by the first administration of study treatment.

Replacement of subjects may occur in Part A in order to ensure the necessary number of evaluable subjects for dose selection (at least 4 subjects per tested dose level, a total of 20 evaluable subjects) and to ensure at least 26 valid subjects for assessment of the RP2D. Subjects maybe replaced in the following circumstances:

Dose selection:

- Subjects who discontinue or took less than 80% of the per protocol required total dose of either study drug (rogaratinib or atezolizumab) during the first cycle due to any reason other than a DLT (*note*: protocol-defined dose reductions will not be considered incompliant).

Efficacy:

- Subjects who took less than 80% of the per protocol required total dose of either study drug (rogaratinib or atezolizumab) during the first two cycles or subjects without an efficacy assessment.

4.3 Handling of Missing Data

Missing data will not be replaced. Analyses will be performed considering all data observed for the respective analysis sets.

All missing or partial data will be presented in the subject data listing as they are recorded on the Case Report Form.

4.4 Interim Analyses and Data Monitoring

Safety data will be reviewed on an ongoing basis during this study. Additional analysis, as Bayesian dose-response and / or PK / PD modeling of DLTs rates and CTCAE version 4.03 gradings may be performed on selected groups of subjects in order to generate additional relevant information for the adaptive dose selection decisions. The sponsor together with all investigators will review all available data and make the final decision as to dose escalation, de-escalation or group expansion during the adaptive dose selection part. This group of sponsor and investigators will also determine when to implement predefined stopping rules.

No formal interim analysis of the data collected during Part A is planned.

4.5 Data Rules

4.5.1 Baseline

The baseline values will be the latest valid pre-administration available value.

4.5.2 Repeated Measurements

If control measurements for a planned timepoint before study drug administration are available, the last value (i.e. of the measurement closest to the study drug administration) will be used for the calculation of descriptive statistics. If control measurements for a planned time point after study drug administration are available, the first value (i.e. of the planned measurement) will be used for the calculation of descriptive statistics.

4.5.3 Laboratory Values Outside the Calibration Range

Means at any time will only be calculated if at least 2/3 of the individual data were measured and were above the lower limit of quantification (LLOQ). For the calculation of the mean value a data point below LLOQ will be substituted by one half of this limit. In tables showing

mean values, where values below LLOQ are included in the calculation of mean values, these means will be marked. Differences (e.g. changes from baseline) will only be calculated if at least one measurement is not substituted.

4.6 Blind Review

This phase 1 study is performed in a non-blinded design because this is considered adequate to meet the study objectives.

The results of the validity review meeting will be documented in the Validity Review Report and may comprise decisions and details relevant for statistical evaluation. Any changes to the statistical analysis prompted by the results of the validity review meeting will be documented in an amendment and, if applicable, in a supplement to this SAP or will be documented in the clinical study report.

5. Analysis Sets

5.1 Assignment of analysis sets

Final decisions regarding the assignment of subjects to analysis sets will be made during the review of study data and documented in the final list of important deviations, validity findings and assignment to analysis set(s) (see section **4.6**).

All subjects who signed the informed consent form (ICF) for FGFR testing will be included in the 'All enrolled subjects' evaluations. All subjects assigned to treatment will be included in the 'All subjects assigned to treatment' evaluations.

Safety analysis set (SAF)

All subjects who received at least one dose of study drug (i.e. rogaratinib or atezolizumab) and have post-treatment safety data available will be included in the safety evaluation.

MTD analysis set (MTD)

All subjects who completed Cycle 1 and who took at least 80% of the required total dose (protocol-defined dose reductions will not be considered incompliant) of either study drug (rogaratinib or atezolizumab) during Cycle 1 or discontinued during Cycle 1 due to a DLT will be included in the MTD evaluation.

Only subjects from the dose selection part are to be considered for the MTD analysis set.

Efficacy analysis set (EFS)

All subjects who have received at least one dose of study drug and who have post-baseline efficacy data available will be included in the efficacy evaluation.

Pharmacokinetics analysis set (PKS)

All subjects who have received at least one dose of study drug and with at least one valid concentration after first dosing and no important protocol deviations affecting the validity will be included in the PK evaluation.

6. Statistical Methodology

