10.2 Analysis sets

Safety analysis set (SAF)

All patients who received at least 1 dose of study drug and have post-treatment safety data available will be included in the safety evaluation.

MTD analysis set

All patients who completed Cycle 1 and who took at least 80% of the required total dose (protocol-defined dose reductions will not be considered incompliant) of either study drug (rogaratinib or atezolizumab) during Cycle 1 or discontinued during Cycle 1 due to a DLT will be included in the MTD evaluation.

Efficacy analysis set

All patients who have received at least 1 dose of study drug and who have post-baseline efficacy data available will be included in the efficacy evaluation.

Pharmacokinetics (PK) analysis set (PKS)

All patients who have received at least 1 dose of study drug and with at least 1 valid concentration after first dosing and no important protocol deviations affecting the validity will be included in the PK evaluation.

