10.3.3.1 Secondary efficacy variable

The secondary efficacy variable is objective response rate.

Objective response rate (ORR) is defined as the percentage of patients whose best response is either a complete response (CR) or partial response (PR). Patients for whom best tumor response is not CR or PR, as well as patients without any efficacy assessment will be considered non-responders. According to RECIST v1.1, confirmation of PR and CR is not required considering the nature of the study and the protocol requirements.

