6.2 Efficacy

Efficacy analyses will be performed on the EFS, unless otherwise specified.

All efficacy variables evaluated using the Response Evaluation Criteria in Solid Tumors (RECIST) version 1.1 are linked to the secondary and exploratory objectives of the study Part A. All variables evaluated using the Response Evaluation Criteria in Solid Tumors Modified for Immune-based Therapeutics (iRECIST) version 1.1 are exploratory only.

Efficacy data will be summarized using descriptive statistics and will be graphically displayed if appropriate. The correlation between pharmacodynamic parameters and selected safety, efficacy, or PK parameters may be graphically displayed. Further statistical analyses may be conducted.

Response as defined by RECIST version 1.1: complete response (CR), partial response (PR), stable disease (SD), progressive disease (PD). Response and progression will be evaluated in this trial using the new international criteria proposed by the RECIST committee for solid tumor.

iRECIST defines new response categories, including iUPD (unconfirmed progressive disease) and iCPD (confirmed progressive disease). For purposes of iRECIST assessment, the first visit showing progression according to RECIST 1.1 will be assigned a visit (overall) response of iUPD, regardless of which factors caused the progression.

Best overall tumor response according to RECIST criteria will be summarized using frequency counts. Best % change in Target Lesion sum of diameter from baseline will be displayed graphically for all subjects from worst to best in a waterfall plot.

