6.2.2 Secondary Efficacy Variable

The efficacy variable linked to the secondary objective of this study is the objective response rate.

Objective response rate (ORR) is defined as the percentage of subjects whose best response is either a CR or PR. Subjects for whom best tumor response is not CR or PR, as well as subjects without any efficacy assessment will be considered non-responders. According to RECIST version 1.1, confirmation of PR and CR is not required considering the nature of the study and the protocol requirements.

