6.2.3 Exploratory Efficacy Variables

Exploratory efficacy variables defined according to RECIST version 1.1 will include disease control rate (DCR), duration of response (DOR), progression-free survival (PFS) (according to both RECIST and iRECIST), time to progression (TPP), time to response (TTR), overall survival (OS) and follow-up time.

These variables are defined as below:

Follow-up time is defined as the time from the date of first study treatment until death or the date of last contact, if the subject is still alive at the time of analysis.

Disease control rate (DCR) is defined as the percentage of subjects whose overall best response was not progressive disease (i.e. CR, PR, SD or Non CR/Non PD). Tumor assessments with SD as response, that is performed prematurely after assignment to treatment of the subject (i.e. substantially earlier than the first planned radiological tumor assessment at 9 weeks), will not be taken into account.

Duration of response (DOR) (for PR and CR) is defined as the time (days) from the first documented objective response of PR or CR, whichever is noted earlier, to disease progression or death (if death occurs before progression is documented). DOR will be defined for responders only, i.e. subjects with a CR or PR. The actual dates the tumor scans were performed will be used for this calculation. DOR for subjects who have not progressed or died at the time of analysis will be censored at the date of their last tumor assessment.

Kaplan-Meier (KM) product-limit estimates for median, 25th and 75th percentile with its 95% CI together with total number of subjects, total censored and total events will be provided for DOR per dose group. In addition KM survival curves will be presented for each dose group.

Progression-free survival (PFS) is defined as the time (days) from start of study treatment to date of first observed disease progression (investigator's radiological or clinical assessment) or death due to any cause, if death occurs before progression is documented. The actual date that the tumor scan was performed will be used for this calculation. If a tumor assessment is performed over more than one day (e.g. scans for chest and abdomen done on different days for the same evaluation), the earliest date will be used for the calculation of PFS. For subjects without documented radiological or clinical progression or death at the time of analysis, PFS will be censored at the last actual visit date of tumor evaluation.

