Kaplan-Meier (KM) product-limit estimates for median, 25th and 75th percentile with its 95% CI together with total number of subjects, total censored and total events will be provided for PFS per dose group. In addition KM survival curves will be presented for each dose group.

Overall survival (OS) is defined as the time (days) from start of study treatment to death due to any cause. Subjects alive at the date of data cut-off for analysis will be censored at the last date known to be alive. If a subject is lost to follow-up before any assessment after assignment to treatment, this subject will be censored at day 1.

KM product-limit estimates for median, 25th and 75th percentile with its 95% CI together with total number of subjects, total censored and total events will be provided for OS per dose group. In addition KM survival curves will be presented for each dose group.

Time to progression (TTP) is defined as the time (days) from start of study treatment to date of first observed disease progression (radiological or clinical). TTP for subjects without disease progression at the time of analysis will be censored at the last date of tumor evaluation. TTP for subjects who have no tumor assessments after baseline will be censored at day 1.

KM product-limit estimates for median, 25th and 75th percentile with its 95% CI together with total number of subjects, total censored and total events will be provided for TTP. In addition KM survival curves will be presented for each dose group.

Time to Response (TTR) is defined as the time (days) from start of study treatment to the date of first observed partial or complete response. Only subjects with a partial or complete response are considered for TTR.

KM product-limit estimates for median, 25th and 75th percentile with its 95% CI together with total number of subjects, total censored and total events will be provided for TTR. In addition KM survival curves will be presented for each dose group.

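### The efficacy set and the ORR non-responder rule do not fit together: if the default set applies and efficacy data means a tumor assessment, unassessed patients drop out of the ORR denominator

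*SAP*

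**What the plan says.** - **Analysis set.** SAP 5.1 admits "All subjects who have received at least one dose of study drug and who have post-baseline efficacy data available". Protocol 10.2 has the same condition: treated patients "who have post-baseline efficacy data available will be included in the efficacy evaluation". Neither document says whether the data must be a scan, or whether clinical progression or survival status is enough.
- **Default.** SAP 6.2: "Efficacy analyses will be performed on the EFS, unless otherwise specified". The ORR section that follows names no other set.
- **ORR rule.** SAP 6.2.2: "subjects without any efficacy assessment will be considered non-responders". Protocol 10.3.3.1: "patients without any efficacy assessment will be considered non-responders".
- **Neighbouring rules.** SAP 6.2.3 states for time to progression: "TTP for subjects who have no tumor assessments after baseline will be censored at day 1". For overall survival, SAP 6.2.3 and protocol 10.3.3.2 censor at day 1 a patient who is lost before any assessment after assignment to treatment.
- **Replacement.** Protocol 6.4.2 and SAP 4.2 allow replacement of patients without an efficacy assessment, and of patients who took less than 80% of the required dose of either drug in the first two cycles.
- **Timing.** SAP 5.1 leaves the final assignment of patients to sets to the review of study data. The trial is open-label.

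**The concern.** The set definition and the ORR rule treat the same patients differently. A patient who is treated but never scanned after baseline is a non-responder under the ORR rule. On one reading of the set definition, the same patient is not in the analysis at all. Such a patient cannot be a responder, so leaving the patient out can only raise ORR.

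Protocol 10.3.3.1 and SAP 6.2.2 name ORR as the secondary efficacy variable, although protocol 9.4 also calls other response variables secondary. In a single-arm trial there is no comparator to absorb a change of denominator, so the denominator directly sets the reported rate. Because sets are finalised during review of open-label data, the choice could be made after responses are known.

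**Working it through.** **1. The plan's own figures.** Protocol 10.4 uses a Jeffreys prior, Beta(0.5, 0.5), and 26 evaluable patients.
- Lower criterion, at most 7 of 26 responders: P(π ≤ 0.4 | data) = 0.916, and P(X ≤ 7 | 26, 0.15) = 0.968. The plan states at least 91% and at least 96%.
- Upper criterion, at least 14 of 26 responders: P(π > 0.4 | data) = 0.924, and P(X ≥ 14 | 26, 0.6) = 0.801. The plan states at least 92% and 80%.
- Total with 15% dropout: 26 × 1.15 = 29.9, or 26/0.85 = 30.6. The plan states approximately 30.

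The figures reproduce, and they are stated for evaluable patients.

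**2. Which reading of the set?** There are three.
- (a) Efficacy data means a post-baseline tumor assessment, and the default set applies. Unassessed patients are out, and that half of the ORR rule is empty. Patients with a scan but no CR or PR still count as non-responders.
- (b) Efficacy data includes clinical progression or death. The PFS definition counts both, since its event is the "date of first observed disease progression (investigator's radiological or clinical assessment) or death due to any cause". Unassessed patients with such data stay in, and the inflation shrinks or disappears.
- (c) The ORR rule is itself the exception that SAP 6.2 allows. All treated patients are in, and there is no inflation.

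The replacement rule and the use of evaluable patients in protocol 10.4 lean towards (a). The replacement rule does not settle it, because it also covers under-dosed patients, whom the set definition does not exclude. The ORR, TTP and OS rules lean towards (b) or (c).

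**3. Size under (a).** Let n be all treated, k the treated patients without a post-baseline tumor assessment, and r the responders. The k patients contribute no responders, so

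[r/(n-k)] / [r/n] = n/(n-k), exactly.

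The documents do not give k. Assumption: n = 30 (the planned total) and k = 1 to 5. Two responder counts serve as examples: 7, because 7/30 = 23.3% is close to the 23% for atezolizumab alone in protocol 3.4; and 12, because 12/30 is the 40% threshold of protocol 10.4.

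| k | factor 30/(30-k) | 7 responders (23.3% of 30) | 12 responders (40.0% of 30) |
|---|---|---|---|
| 1 | 1.03 | 7/29 = 24.1% | 12/29 = 41.4% |
| 2 | 1.07 | 7/28 = 25.0% | 12/28 = 42.9% |
| 3 | 1.11 | 7/27 = 25.9% | 12/27 = 44.4% |
| 4 | 1.15 | 7/26 = 26.9% | 12/26 = 46.2% |
| 5 | 1.20 | 7/25 = 28.0% | 12/25 = 48.0% |

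k = 4 corresponds to every planned dropout (30 - 26) being unassessed. That is probably pessimistic: SAP 4.2 defines a dropout as any premature discontinuation after the start of treatment, and many such patients will have been scanned.

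**4. Can k be above zero?** Yes. Protocol 9.4 sets at least 9 weeks before the first on-treatment scan, so early death or loss can precede it. The end-of-treatment scan (protocol 9.2.2.5) closes most of the gap. It is waived, however, when the previous evaluation was within 4 weeks (up to week 18), and as worded a screening scan could satisfy that for a very early stop.

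**The case against.** The strongest reply is that a plan should be read so that every clause has effect. The ORR rule, the TTP rule and the OS rule all provide for patients without assessments. Reading (a) empties the ORR and TTP clauses and, in large part, the OS clause, while the exception wording in SAP 6.2 leaves room for (c). Efficacy is exploratory throughout (SAP 4.1), and exclusions from each set are tabulated with reasons (SAP 6.1.1). The validity review is documented (SAP 4.6). Patients who stop without radiological progression are scanned at end of treatment and, up to primary completion, in follow-up. All of this stands, and it makes the point minor. It does not remove the point: no sentence states the ORR denominator, and a table of exclusions shows who was left out without fixing the denominator in advance.

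A reader might also draw three stronger inferences that the documents do not support.
- **That a protocol 10.4 verdict is at risk.** With k = 4, 14 responders give P(π > 0.4) = 0.924 on 26 patients and 0.773 on 30, which straddles the 92% mark. But those criteria are written for evaluable patients, and the SAP states no decision rule on them. The shift is not harm caused by this conflict.
- **That disease control rate has the same gap.** The opening words, "the percentage of subjects whose overall best response was not progressive disease", look open. The same sentence then limits disease control to CR, PR, SD or the non-CR/non-PD category, and an unassessed patient has none of these.
- **That PFS, TTP or OS is biased.** No such bias is shown, and TTP and OS already have rules for unassessed patients.

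**Conclusion.** The conflict is real, conditional and minor. Under reading (a), ORR is multiplied by exactly n/(n-k), or 1.03 to 1.20 for the assumed n = 30 and k = 1 to 5. Under (c), or with k = 0, there is no inflation; under (b) there is little or none. The documents do not settle the reading, but the balance of their own rules suggests that unassessed patients were meant to be counted. The planned scans should keep k towards the low end of the range. No confirmatory conclusion is affected.

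**What to change.** - State in SAP 6.2.2 and protocol 10.3.3.1 that the ORR denominator is all patients who received at least one dose of study drug, including replaced patients, with unassessed patients counted as non-responders.
- Report ORR in patients with at least one post-baseline tumor assessment as a labelled sensitivity analysis.
- Keep the protocol 10.4 criteria labelled as applying to evaluable patients. Applied to all 30 treated with 4 unassessed, the upper criterion would need 16 responders instead of 14 (15/30 gives 0.868, 16/30 gives 0.931). The chance of meeting it at a 0.6 response rate among the 26 assessed would fall from 80.1% to 52.1%.
- If data have already been reviewed (protocol 15.3 mentions safety data from a July 2021 cut), document the clarification as made after the data cut and report both denominators.
- Make no change for DCR, PFS, TTP or OS.

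The cost is a wording change in both documents, one extra ORR line and, where data have been seen, the need to label the change as post-data. No new visits or data are required. The reported ORR may be slightly lower.
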